In September 2015, a new FDA-approved test became available at Beaumont, computed tomography-derived fractional flow reserve (CT-FFR, provided by HeartFlow, Inc.), that provides flow information directly from computational fluid dynamic analysis of CCTA images without further testing^{7- 15}. This analysis does not involve any additional imaging, contrast or medications. CT-FFR has been shown to be more accurate in predicting the presence of true ischemia on invasive fractional flow reserve testing in the invasive catheterization laboratory (CATH-FFR). Patients managed by CATH-FFR have been shown to have better outcomes than patients managed using visual inspection of CATH stenosis alone. The standard cutoff for an abnormal CATH-FFR and CT-FFR is the measurement of a blood pressure drop of $\geq 20\%$ (FFR ≤ 0.80) across a given stenosis.

For Beaumont ED patients, CT-FFR has been in use on a research basis since September, 2015, but is not considered standard of care. Since September 2015 we have conducted a study to analyze clinical outcomes after CT-FFR, (a sub-analysis of HIC #2016-157, the Beaumont CT Registry). We have collected, analyzed data and submitted for publication, data on 147 ED patients with CCTA stenosis of 25-99% managed with CT-FFR and followed for a minimum of 90 days. These data show no evidence to date of increased risk, but do show improved prediction of the need for revascularization using CT-FFR (see Appendix, submitted for publication).

The objective of the present trial is to evaluate the CATH rate and diagnostic effectiveness of CT-FFR as compared to a standard of care diagnostic strategy (SOC) in the management of ACP patients with intermediate-to-severe stenosis on CCTA.

Hypotheses:

Primary Hypothesis:

Cardiac Catheterization Rate: Use of CT-FFR will reduce the CATH rate in ACP patients with >50% stenosis on CCTA. There will be a pre-specified subset analysis of the Intermediate (51-70%) and Severe (71-90%) stenosis groups.

Secondary Hypotheses:

1. Diagnostic Effectiveness: CT-FFR results will more accurately triage patients to CATH compared to patients triaged by SOC. True flow-limiting coronary stenosis will be defined by CATH-FFR as the gold standard in patients undergoing CATH. Accurate triage will be calculated as the proportion of patients with correct triage to CATH based on CATH-FFR results:

CT-FFR group:

True positive case: CT-FFR positive and CATH-FFR positive

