True negative case: CT-FFR negative and CATH-FFR negative

Proportion of correct CT-FFR triage = (True positive + True negative) / All CATH

SOC group:

True positive case: SOC chosen by attending physician for CATH confirmed by CATH-FFR. By definition, the clinicians' decision to CATH based on clinical evidence is considered an SOC positive case, there can be no SOC true negative cases that go to CATH.

Proportion of correct SOC triage = True positive / All CATH

2. Safety: Patients following CT-FFR-guided management will have similar MACE rates, including death, ACS and unanticipated late revascularization when compared to SOC-guided patients.

Methods

Study Population

The study population will be drawn from ED ACP who have already undergone CCTA for diagnosis, and have been found to have 50% or greater stenosis but less than 90% of at least one coronary branch. Two-hundred patients meeting entry criteria will be enrolled from a sample of ED ACP patients at Beaumont Hospital (Royal Oak). These patients will be randomized 1:1 using sealed envelopes provided by the study statistician, to either standard of care (SOC) or CT-FFR management. (See Figure 1. Study Diagram)

Inclusion Criteria

1. Emergency department or inpatients admitted through the ED with chest pain suspicious for ACS based on history and physical examination.
2. At least one biomarker (troponin) and electrocardiogram with no evidence of definite ACS.
3. A completed CCTA demonstrating $\geq 50\%$ but $< 90\%$ stenosis of at least one coronary artery branch.
4. CCTA test images with sufficient diagnostic quality for CT-FFR analysis.
5. Ability and willingness to provide informed consent.

Exclusion Criteria

- 1 Left main coronary stenosis of 50% or greater.
- 2 CCTA lesions demonstrating stenosis >90% ("subtotal"), or complex, high-risk plaque characteristics resulting in an a priori recommendation for triage to CATH by CCTA interpreting physician.
- 3 Attending physician a priori decision for CATH.
- 4 Prior coronary stent, coronary bypass or prior known myocardial infarction.
- 5 Clinical instability, such as hypotension, signs of shock, and/or unrelieved or accelerating chest pain.
- 6 Pregnancy

Obtaining Consent

Consent will be obtained by a co-investigator. Patients will have at least 20 minutes to consider whether they wish to consent.

Screening Log

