Attending physicians will dictate SOC management according to their own clinical judgment. This could include discharge without further testing, EKG-only stress testing, stress echocardiography, stress myocardial perfusion imaging, direct admission and further noninvasive testing or CATH. In addition to standard testing, a blinded CT-FFR will be obtained for post hoc analysis, but it will not be used for patient management. Image data from our CT workstation will be sent directly to HeartFlow, Inc. over a secure research transfer node.

If attending physicians decide that SOC Group patients should undergo CATH, the protocol will specify an invasive fractional flow reserve will be performed on all lesions over 30% stenosis severity, to confirm the presence or absence of flow-limiting stenosis. This may be waived without protocol deviation if deemed unsafe by the severity of stenosis or due to clinical circumstances, as documented in a completed Physician Study Questionnaire.

CT-FFR-Guided Group Management

Patients in this group will be triaged using CT-FFR. Image data from our CT workstation will be sent directly to HeartFlow, Inc. over a secure Priority (STAT) transfer node. Interpreting physician will categorize CT-FFR results as follows:

1. CT-FFR >0.80. All CT-FFR segmental values are >0.80, with no indication of flow limiting ischemia. A non-binding recommendation that the patient undergo an initial trial of medical therapy will be made by the interpreting co-investigator. Attending physicians will be asked to complete a study Physician Questionnaire to determine whether they followed this recommendation or not, and if not, why not.
2. CT-FFR 0.70-0.80. These will be reported as values in the abnormal range without specific recommendations about whether CATH should be performed. Attending physicians will decide triage in consideration with other clinical data. Attending physicians will be asked to complete a study Physician Questionnaire to determine what clinical factors influenced their triage decision.

3. CT-FFR <0.70. These are abnormal values that are will be reported as high-risk. A non-binding recommendation that the patient undergo CATH will be made by the interpreting co-investigator. Attending physicians will be asked to complete a study Physician Questionnaire to determine whether they followed this recommendation or not, and if not, why not.

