Risks Associated with Heart Catheterization and Invasive Fractional Flow Reserve

Common (more than 10%)

- warm feeling or flushed feeling during adenosine infusion (which is part of the FFR study)
- lightheadedness
- nausea
- pain
- discomfort
- bruising or bleeding where the catheter is inserted in the groin
- radiation equivalent to 3-5 years of natural background radiation

Rare (less than 1%)

- contrast (dye) allergy
- diaphoresis (temporary excessive sweating)
- atrioventricular block -impaired conduction of the impulse that regulates the heartbeat (from adenosine)
- contrast induced nephropathy (deterioration of kidney function due to contrast exposure)
- hives (for those allergic to contrast dye)
- thrombosis (blood clots resulting in reduced blood flow)
- artery dissection (damage to the artery wall)
- perforation (a hole in the artery)
- stroke
- myocardial infarction (heart attack)
- death

Internal Safety Monitoring Committee

An Internal Safety Monitoring Committee will conduct regularly scheduled reviews of the safety of patients. Two physicians and a statistician who are not co-investigators will be included. Members will monitor safety outcomes, enrollment and completeness of follow-up. The Committee will meet after the first 20 patients and after each 40 subsequent patients till the study is completed. Any MACE event or major adverse outcome will be reported immediately to the Committee. The results of all Committee meetings will be provided to the IRB.

Data Analysis

Descriptive statistics will be given for all variables collected including indications for the test, demographics, patient history, CTA tech information, details from the physicians reading form, and from the CT-FFR. Missing data will remain missing and will not be replaced by substitutions or interpolation. Categorical variables will be summarized as counts and percentages. All continuous variables will be

summarized as means+/- the standard deviation where normal or median and 25th, 75th percentiles if not normal. The minimum and maximum will also be provided.

Catheterization Rate: The primary outcome will be examined between the 2 randomization arms using Pearson's Chi-square test. The Odds ratio and 95% confidence interval will also be reported.

Diagnostic Effectiveness: The secondary outcome will be defined as the proportion of accurate triage using CATH-FFR as the gold standard among all patients triaged to CATH by each strategy.

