The SOC group will be analyzed according to actual triage decisions, as well as the hypothetical results of triage using a blinded CT-FFR analysis collected on those patients. The accuracy of triage between these two methods will then be compared.

Safety: The secondary outcome will be safety, as defined by the incidence of death, ACS or late unscheduled revascularization in each group.

Additional data analysis:

The Total length of stay, with sub-analysis of ED and inpatient length of stay will be reported as medians, 25th and 75th percentiles and minimum to maximum. The 2 randomization arms will be examined for each of these using Wilcoxon rank sum tests.

The hospital admission rate, the proportion of patients going to CATH in either arm who are found to have significant coronary stenosis (>50 stenosis), proportion of patients going to CATH who have a positive invasive FFR, percentage of patients undergoing PCI or CABG within 3 months, secondary diagnostic testing during index visit or within 3 months follow-up, including: recurrent ED visits, inpatient admissions for suspected acute coronary syndromes and/or CATH, outpatient or inpatient evaluation with cardiac CCTA or stress testing, cardiac surgery or PCI and MACE events (including all cause death, acute myocardial infarction, acute coronary syndromes, unscheduled revascularization after index visit) will be examined between the 2 arms using Pearson's Chi-square test where appropriate (Expected frequency>5 in all cells), otherwise Fisher's Exact tests will be used. The Odds ratios and 95% confidence intervals will also be reported.

[figure not shown]
Estimated costs of care: including all estimated charges based on Beaumont hospital analysis multiplied by the standard Medicare cost/charge ratio will be reported as medians, 25th and 75th percentiles and minimum to maximum. The 2 randomization arms will be examined using Wilcoxon rank sum tests.

We may explore possible associations between patient characteristics demographics, prior history or testing indications and the randomization groups, safety outcomes,

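### Diagnostic effectiveness is scored only in catheterised patients, so it measures yield per CATH and cannot by itself show that CT-FFR triages more accurately

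*Combined protocol and SAP*

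**What the plan says.** The first secondary hypothesis is that "CT-FFR results will more accurately triage patients to CATH compared to patients triaged by SOC". The reference standard exists only at catheterisation: "True flow-limiting coronary stenosis will be defined by CATH-FFR as the gold standard in patients undergoing CATH".

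The two scores under Secondary Hypotheses share one denominator:

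- CT-FFR arm: "Proportion of correct CT-FFR triage = (True positive + True negative) / All CATH"
- SOC arm: "Proportion of correct SOC triage = True positive / All CATH", with the explanation that "there can be no SOC true negative cases that go to CATH"

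The Data Analysis section repeats the restriction: accuracy is assessed "among all patients triaged to CATH by each strategy". The list under Additional data analysis includes a closely related quantity, the "proportion of patients going to CATH who have a positive invasive FFR".

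Who is catheterised depends on the arm. In the control arm, "Attending physicians will dictate SOC management according to their own clinical judgment". In the CT-FFR arm, the attending physician decides after seeing the CT-FFR category and, in the top and bottom categories, a non-binding recommendation (CT-FFR-Guided Group Management).

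Two other planned analyses bear on the point. Within SOC, actual triage is to be compared with the triage that a blinded CT-FFR would have given. MACE, PCI or CABG, and repeat testing are to be compared between the full arms.

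**The concern.** Triage accuracy has two sides: sending patients with flow-limiting stenosis to CATH, and keeping the others away. A score over catheterised patients sees only what happened to those who were sent. A patient with flow-limiting disease who is never catheterised is in neither numerator nor denominator, and nor is a patient without it who was rightly spared.

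The denominator is also the thing the trial sets out to change. If the primary hypothesis succeeds, the two catheterised groups will differ in size and in how they were selected, and the comparison will no longer be between randomised groups. A higher CT-FFR score would then be reported as more accurate triage when it shows a higher yield per CATH. Giving both arms the same formula and obtaining CATH-FFR in every CATH patient would not remove this problem.

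**Working it through.** **Planned CATH rates (Sample Size).** The plan weights the 51-70% and 71-99% stenosis groups 2:1.

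- SOC: (2 × 58.3 + 89.5)/3 = 68.7%, as stated.
- CT-FFR: (2 × 21.3 + 65.6)/3 = 36.1%, as stated. The chosen 87 per arm uses 45%.

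The plan gives no expected value or power for diagnostic effectiveness, so there is no stated figure to reproduce for the outcome itself.

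**Illustration.** Assumptions not in the documents: 100 patients per arm, 40 FFR-positive in each, CATH-FFR complete at every CATH. To isolate the denominator, the SOC formula (FFR-positive CATHs / all CATHs) is used in both arms. CATH counts follow the planning rates; the numbers found are assumed. For C CATHs that find T of the 40:

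- score = T/C
- missed = 40 − T
- FFR-negative CATHs = C − T
- correct over the whole arm = T + [(100 − C) − (40 − T)]

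| Arm | C | T | Score | Missed | FFR-negative CATHs | Correct per 100 |
|---|---|---|---|---|---|---|
| SOC | 69 | 38 | 55.1% | 2 | 31 | 67 |
| CT-FFR | 36 | 22 | 61.1% | 18 | 14 | 68 |
| CT-FFR | 45 | 25 | 55.6% | 15 | 20 | 65 |
| CT-FFR | 36 | 30 | 83.3% | 10 | 6 | 84 |
| CT-FFR | 45 | 38 | 84.4% | 2 | 7 | 91 |

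Row 2 scores higher than SOC with equal whole-arm accuracy to within one patient. Row 3 scores slightly higher than SOC with lower whole-arm accuracy. Rows 4 and 5 have nearly the same score, but one leaves 10 of 40 uncatheterised and the other 2.

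**Break-even.** The CT-FFR arm matches the SOC score once it finds 0.551 × 36 = 19.8, so 20 of 40, with 36 CATHs; or 0.551 × 45 = 24.8, so 25 of 40, with 45 CATHs.

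**Range of assumed prevalence.** SOC catheterises 95% of its FFR-positive patients in 69 CATHs; CT-FFR catheterises 60% in 36.

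| FFR-positive per 100 | Score, SOC vs CT-FFR | Missed, SOC vs CT-FFR | Correct per 100, SOC vs CT-FFR |
|---|---|---|---|
| 30 | 41.3% vs 50.0% | 1.5 vs 12 | 58 vs 70 |
| 40 | 55.1% vs 66.7% | 2 vs 16 | 67 vs 72 |
| 50 | 68.8% vs 83.3% | 2.5 vs 20 | 76 vs 74 |

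CT-FFR scores higher in all three rows. Whole-arm accuracy agrees with that ranking in the first two and reverses it in the third.

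**Precision.** For 22/36 against 38/69 the difference is 6.0 points, with standard error √(0.611 × 0.389/36 + 0.551 × 0.449/69) = 0.101 and 95% CI about −14 to +26 points.

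**The same data per 100 randomised.** FFR-positive CATHs: 38 vs 22, difference 16, standard error √[(0.38 × 0.62 + 0.22 × 0.78)/100] = 0.064, 95% CI about 3.5 to 28.5. FFR-negative CATHs: 31 vs 14, difference 17, standard error √[(0.31 × 0.69 + 0.14 × 0.86)/100] = 0.058, 95% CI about 5.7 to 28.3. Both the disease not found and the CATHs avoided become visible.

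**The case against.** A reader might infer that missed disease never counts anywhere in this plan, or that the illustration shows CT-FFR missing nine times as many cases as SOC (18 vs 2). The documents support neither.

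- **The comparison within SOC exposes some CT-FFR misses.** Both methods are applied to the same patients, and CT-FFR did not choose who was catheterised. An SOC patient who is CT-FFR negative but CATH-FFR positive is the kind of case that CT-FFR guidance would tend to leave uncatheterised, and it is seen here. This stands, with one limit: disease that SOC itself left uncatheterised stays unseen.
- **Some errors enter the CT-FFR score.** Recommendations are non-binding, and the Sample Size section reports CATH in 21.3% and 65.6% of earlier CT-FFR-negative patients in the two stenosis groups. A catheterised CT-FFR-negative patient with a positive CATH-FFR counts as an error. The formulas set no time window for CATH, so a later CATH might also count.
- **Consequences are measured in everyone.** MACE and revascularisation cover all patients, but as separate outcomes. They do not alter the accuracy figure.
- **The yields are assumed.** The nine-fold ratio follows only from supposing that SOC finds 38 of 40 and CT-FFR 22. The resulting 6-point difference has an interval from −14 to +26 and would not itself establish superiority.
- **Earlier CATH rates were similar** (58% and 54%, Risks of the Study). Similar rates would shrink the distortion, but they are not what the primary hypothesis and the sample size expect.
- **Uncatheterised patients have no reference standard, and the plan says so openly.** True. Whole-arm accuracy cannot be observed in this design. That limits what can be claimed; it does not turn a per-CATH proportion into triage accuracy.

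Nor do the documents show that CT-FFR would select only the more obvious cases: the arm selects on flow values, with no recommendation at 0.70-0.80.

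**Conclusion.** The concern holds for the between-arm outcome. The score conditions on a post-randomisation subset that the plan expects to differ sharply in size (68.7% vs 36% to 45%), and it has no term for uncatheterised patients. It is a yield per CATH and does not by itself support the first secondary hypothesis.

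Under the stated assumptions, a CT-FFR arm finding 20 of 40 FFR-positive patients in 36 CATHs, or 25 of 40 in 45, would score as well as an SOC arm finding 38 of 40 in 69. How far the result would mislead in practice is unknown, because prevalence and yields are not given. It should not be inferred that CT-FFR will miss more disease, or that a higher score would be wrong: in the last row of the first table CT-FFR leads on both measures. The point is that the score cannot tell these cases apart.

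The outcome is secondary and has no stated power, but it carries the trial's accuracy claim, so the change should be made. The unequal formulas (true negatives credited only to CT-FFR) and waived CATH-FFR are separate matters.

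**What to change.** For the between-arm comparison, use all randomised patients as the denominator and state the time window for CATH. Report per arm, with difference and 95% CI:

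- (a) CATHs with CATH-FFR done and no positive lesion, including those with no lesion above 30%;
- (b) CATHs with a CATH-FFR-positive lesion;
- (c) CATHs with CATH-FFR waived or missing, as a category of its own, so that a waiver for severe stenosis is not counted as an unnecessary CATH. Add a sensitivity analysis that classes those waived for severe stenosis as positive.

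Read (a) and (b) together, since both fall when fewer patients are catheterised. Randomisation balances disease in expectation, so the difference in (b) estimates the difference in disease found, subject to (c).

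Among patients not catheterised at index, report by arm later ACS, CATH-FFR-positive CATH or revascularisation within the planned follow-up, as a descriptive indicator of missed disease.

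Keep the per-CATH proportion as a descriptive yield of CATH. Keep the comparison of actual and blinded CT-FFR triage within SOC as the within-patient accuracy analysis, and state its verification limit. Do not rest the claim of more accurate triage on the per-CATH proportion alone.

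Cost: revised SAP wording and a few more table rows from data already planned. The single headline accuracy figure is lost.

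### The within-SOC comparison of actual triage with hypothetical CT-FFR triage can be scored only in SOC patients who had CATH, so it does not compare triage methods and never counts CATHs that CT-FFR would have added

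*Combined protocol and SAP*

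**What the plan says.** All references are to the combined protocol and SAP.

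- **Hypotheses, Diagnostic Effectiveness**, fixes the reference standard: "True flow-limiting coronary stenosis will be defined by CATH-FFR as the gold standard in patients undergoing CATH". The CT-FFR rule is "Proportion of correct CT-FFR triage = (True positive + True negative) / All CATH". The SOC rule is true positives over the same denominator, and the text states that a catheterised SOC patient can never be a true negative.
- **Data Analysis** defines the outcome as the proportion of accurate triage "among all patients triaged to CATH by each strategy". It then has the SOC arm assessed on the triage that took place and on the "hypothetical results of triage using a blinded CT-FFR analysis collected on those patients", and adds: "The accuracy of triage between these two methods will then be compared". It names no denominator, paired method or test for this comparison. Missing data are not to be substituted.
- **SOC Group Management** does not limit the blinded test to catheterised patients: "a blinded CT-FFR will be obtained for post hoc analysis, but it will not be used for patient management". It also allows CATH-FFR to be waived in some patients who do have CATH.
- **CT-FFR-Guided Group Management** reports values of 0.70-0.80 as abnormal but "without specific recommendations about whether CATH should be performed".

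**The concern.** This is the plan's only comparison of the two strategies in the same patients, so readers will take it as direct evidence on which one triages better. CATH-FFR exists only where the attending physician chose CATH. The scored set is therefore the set that SOC selected, and every SOC decision in it is positive.

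Two things follow. SOC gets no credit for patients it correctly kept from CATH, while CT-FFR gets credit for each CATH-FFR-negative patient it would have kept from CATH. And SOC patients without CATH whose CT-FFR is abnormal do not appear at all, although their CT-FFR is collected. The comparison can show CATHs that CT-FFR would have avoided but not those it would have added, right or wrong.

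**Working it through.** **Inputs from the documents.** The Sample Size section anticipates a 68.7% SOC CATH rate. This reproduces from its own components at 2:1: (2 × 58.3 + 89.5)/3 = 206.1/3 = 68.7. Risks of the Study gives a historical SOC rate of 58%. The planned arm size is 100. The documents give none of p (CATH-FFR-positive share among catheterised SOC patients), Se or Sp (sensitivity and specificity of CT-FFR in that set). All values of these below are assumptions.

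**Patients left out.** 100 − 68.7 = 31.3, or 100 − 58 = 42 per 100. Waived CATH-FFR can only shrink the scored set further.

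**Scores in the CATH subset, plan's formula.**

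- SOC = p
- CT-FFR = p·Se + (1 − p)·Sp
- CT-FFR − SOC = (1 − p)·Sp − p·(1 − Se), which is positive only if p < Sp/(Sp + 1 − Se)

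| Test (assumed) | CT-FFR score at p = 0.40 (SOC 0.40) | CT-FFR score at p = 0.60 (SOC 0.60) |
|---|---|---|
| Coin flip | 0.50 | 0.50 |
| Always negative | 0.60 | 0.40 |
| Se 0.60, Sp 0.50 | 0.24 + 0.30 = 0.54 | 0.36 + 0.20 = 0.56 |

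The value of p below which CT-FFR scores higher:

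- Se 0.70, Sp 0.60: 0.60/0.90 = 0.67
- Se 0.85, Sp 0.75: 0.75/0.90 = 0.83

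At p = 0.90 the second test scores 0.765 + 0.075 = 0.84 against 0.90 for SOC, a loss of 6 points.

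**Scores if only CT-FFR-positive patients form the CT-FFR denominator.** Yield = p·Se/[p·Se + (1 − p)(1 − Sp)], which exceeds p whenever Se + Sp > 1. For Se 0.60, Sp 0.50 it is 0.24/0.54 = 0.44 at p = 0.40 and 0.36/0.56 = 0.64 at p = 0.60. Under this reading the advantage is automatic.

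**Effect of the omitted patients.** Take 69 SOC patients with CATH (p = 0.60) and 31 without, of whom an assumed 10% are truly positive.

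- Se 0.70, Sp 0.60. CATH only: 0.66 against 0.60, +6 points. Whole arm: SOC 41.4 + 27.9 = 69.3 correct, CT-FFR 45.54 + 18.91 = 64.45, about −5 points.
- Se 0.85, Sp 0.75. CATH only: 0.81 against 0.60, +21 points. Whole arm: SOC 69.3, CT-FFR 55.89 + 23.56 = 79.45, about +10 points.

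The omitted cell can also work the other way. With Se 0.85 and Sp 0.75, its true positives minus false positives are 31 × (0.085 − 0.225) = −4.3 at 10% prevalence and 31 × (0.425 − 0.125) = +9.3 at 50%.

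**CATHs avoided and added.** Assume CT-FFR is abnormal in 60-70% of catheterised SOC patients and 20-50% of the rest.

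| SOC CATH rate | Avoided per 100 | Added per 100 | Net avoided |
|---|---|---|---|
| 68.7% | 68.7 × 0.30 to 0.40 = 20.6 to 27.5 | 31.3 × 0.20 to 0.50 = 6.3 to 15.7 | about 5 to 21 |
| 58% | 58 × 0.30 to 0.40 = 17.4 to 23.2 | 42 × 0.20 to 0.50 = 8.4 to 21.0 | about −4 to 15 |

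The accuracy comparison draws only on the avoided column.

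**The case against.** A reader might infer that the comparison favours CT-FFR by construction, that it cannot come out against any informative test, and that this holds whatever formula is used. The documents do not support that. The only CT-FFR formula they give counts false negatives against CT-FFR, while SOC has perfect sensitivity in the scored set. The weak but informative test above (Se 0.60, Sp 0.50) loses to SOC at p = 0.60, 0.56 to 0.60. The advantage is automatic only with a CT-FFR-positive denominator. The Data Analysis wording could be read that way, but the formula in the Hypotheses section divides by all CATH. An omitted patient with abnormal CT-FFR may also be a true positive that SOC missed, so leaving such patients out can hurt CT-FFR.

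Other points on the plan's side carry some weight:

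- The Data Analysis text refers to the SOC group, not its CATH subset. It also promises descriptive statistics from the CT-FFR and allows exploring CT-FFR categories against CATH. Nothing forbids the fuller table, but that exploration is optional and commits to nothing.
- Net change in CATH use is what the randomised primary outcome measures. That does not make the within-SOC accuracy comparison interpretable.
- The 0.70-0.80 band is a minor gap. The background gives 0.80 or below as the standard abnormal cut-off, the management section calls the band abnormal, and scoring is by positive or negative result. Only an explicit statement for this analysis is missing.
- A table of CATH decisions compares CATH use, not accuracy, so it supplements the stated analysis and does not replace it.

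**Conclusion.** The point holds in a limited form. With CATH-FFR as the only reference, the comparison is confined to patients SOC selected. It gives SOC no credit for CATHs correctly withheld and omits about 31 to 42 of 100 SOC patients, including every CATH that CT-FFR would have added. A metric on which a coin flip or an always-negative test beats clinicians at p = 0.40 cannot by itself show better triage.

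The direction is not fixed. It depends on p, Se, Sp, the denominator chosen and the true disease status of uncatheterised patients. Apart from the CATH rates and arm size, every input to the illustrations is assumed. This concerns one comparison under a secondary outcome. The primary outcome and the sample size are untouched, but the plan should be changed.

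**What to change.** 1. Describe accuracy in the CATH subset as CT-FFR test performance in patients selected by SOC, not as a comparison of triage methods. State its denominator. Report the discordant cells: CATH-FFR-negative CATHs avoided, and CATH-FFR-positive patients missed.
2. Add a cross-tabulation of actual CATH (yes/no) by CT-FFR triage (yes/no) in all SOC patients with a blinded CT-FFR result. Report CATHs avoided, CATHs added and the net change per 100 with a paired (McNemar-type) 95% CI, labelled as a comparison of CATH use. As a guide to precision, the midpoints of the assumed ranges at 68.7% give 24 avoided (68.7 × 0.35) and 11 added (31.3 × 0.35). The net is 13, with standard error √(35 − 13²/100) = 5.8, so the CI runs from about 2 to 24.
3. For this analysis only, count CT-FFR of 0.80 or below as positive in the main table, as the documents' own cut-off implies. Repeat with below 0.70 as a sensitivity analysis.
4. Tabulate follow-up outcomes by CT-FFR result in SOC patients without CATH, using the planned 1-month, 3-month and 1-year contacts.

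The cost is a change of wording and a little more analysis, because blinded CT-FFR, CATH status and follow-up are already planned. The result may look less favourable to CT-FFR.
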